3.0 Study Endpoints/Events/Outcomes

- 3.1 Primary Endpoint/Event/Outcome: Determining the accuracy and precision of a mobile health application (Cap App) to measure CRT in an otherwise healthy pediatric patient population.
- 3.2 Secondary Endpoint(s)/Event(s)/Outcome(s): To establish normal values of CRT via Cap App for healthy children of varying age ranges, determine if subject characteristics such as skin tone, skin temperature, sex, or age affect the CRT measured via the Cap App, and determine if the CRT measured via the Cap App correlates to the manual measurement of CRT in healthy children at varying age ranges.

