Improved access to precise measurement of capillary refill time will help expand the capabilities of experienced providers who are treating patients remotely through telehealth or less experienced providers treating patients in remote locations. This is especially important in low-resource settings or regions remote from specialty centers where providers may not be as experienced in the care of children. Triaging care for conditions such as pediatric dehydration is challenging due to lack of resources, especially in developing countries. However, even in well-developed nations, access to specialized care for pediatric patients is still lacking. Pediatric specialized care in the United States is largely regionalized. Most seriously ill children present first to community hospitals where resources and expertise to treat these children may be limited. In fact, more than 90 percent of emergency department visits for children in the United States are to non-specialty facilities (11). Admission rates for large specialty pediatric hospitals are 2-4 times larger than general emergency departments suggesting that the majority of providers caring for children have limited experience in treating higher acuity pediatric conditions (12). Additionally, in the setting of rising health care costs, many parents and other non-professional caregivers are increasingly seeking health information from non-traditional sources such as mobile smartphones.

- 2.1 Preliminary Data: A pilot study is ongoing on healthy adult volunteers. This study is not yet published in a peer-reviewed journal. The study's main objective is to compare CRT measured from Cap App versus manual visual assessment under differing temperature controls. The study has enrolled 19 participants, age 20-34; 9 female, 10 male. There is some variance in skin tone. We controlled for 5 temperature conditions (30°C, 27.5°C, 25°C, 22.5°C, 20°C) utilizing an ice bath to determine variance of CRT measurement under progressively colder temperatures. The results show that Cap App measures a longer CRT with greater variance in relation to the colder temperatures. It tends to overestimate CRT for darker skin tones. Overall, CRT is longer for Cap App than for a correlated, manual CRT measurement.

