15.3 Statistical Analysis: We will recruit pediatrics patients aged 1 month to 17 years who are presenting to the D2D: The Driven to Discover Research Facility at the Minnesota State Fair. Descriptive statistics will be used to summarize the data collected. For the primary outcome, we will calculate mean CRT along with 95% confidence intervals, both overall and by age group, sex, and skin tone. We will attempt to enroll a minimum of 48 patients per age group for a total of 240 patients. Initial results showed an average standard deviation of 0.663 seconds across all patients at normal hand temperature. When the sample size is 48, a two-sided 95% confidence interval for a mean will extend ± 0.188 seconds. For a total sample size of 240, a two-sided 95% confidence interval for a mean will extend ± 0.084 seconds. Human annotation of a video recording using a stopwatch will be used to measure the manual CRT measurement and we will perform computer annotation of the video recording as a gold standard. For human and computer annotations we will calculate inter-rater reliability by repeating annotations with a different observer on 10% of a random group of CRT measurements. Inter-rater reliability will be evaluated using intraclass correlation coefficients (ICCs) and Bland–Altman plots.

15.4 Data Integrity: The research assistant will obtain study eConsent and fill the data collection forms which will be embedded into the Cap App and will be password protected. The data forms, video recordings for human and computer annotation, and Cap App CRT measurement will then be uploaded to a secure web-based data storage platform, Box. The research assistant will erase the data on the smartphones every shift and will store them in a secure location at all times. The *consent forms, assent forms, and case report forms* will be electronic (UMN REDCap eConsent). No paper copies will be utilized.

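### Section 3.2 asks whether Cap App correlates with manual CRT; correlation cannot show a uniform offset and depends on spread and press noise, and no Cap App versus manual agreement analysis is specified

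*Combined protocol and SAP*

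**What the plan says.** Section 3.1 gives the primary endpoint as "Determining the accuracy and precision of a mobile health application (Cap App) to measure CRT in an otherwise healthy pediatric patient population". Section 3.2 adds, as the last of three secondary aims, to "determine if the CRT measured via the Cap App correlates to the manual measurement of CRT in healthy children at varying age ranges". It names no coefficient and no threshold, and does not say whether the manual value is the human or the computer annotation.

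Section 2.1 describes the pilot: "The study has enrolled 19 participants, age 20-34; 9 female, 10 male". It reports "Overall, CRT is longer for Cap App than for a correlated, manual CRT measurement" and "It tends to overestimate CRT for darker skin tones", without sizes.

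Under 5.1 the two methods time separate compressions: the child's finger on the phone camera for Cap App, and the research assistant's press with transparent plastic for the video. Each method is repeated to give at least four presses per child over both hands. Sections 5.1 and 15.3 call the computer annotation the gold standard.

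Section 15.1 says the methods will be compared within each subject but names no statistic, and it assigns the second to fourth CRT measurements to intra-rater reliability. Section 15.3 analyses the primary outcome as mean CRT with 95% CI, and uses ICCs and Bland–Altman plots for the reliability of repeated annotations only. Its precision statement rests on "Initial results showed an average standard deviation of 0.663 seconds across all patients at normal hand temperature" and "We will attempt to enroll a minimum of 48 patients per age group for a total of 240 patients".

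**The concern.** Correlation is the only named measure that sets Cap App against manual CRT, and it does not answer the question that the pilot raised. The pilot's own summary is of readings that were correlated and yet longer. Asking again whether they correlate could return a high coefficient and leave the offset unmeasured.

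The coefficient also mixes the app's quality with two things that are not the app: how much CRT varies among the children studied, and how much it varies from one press to the next. If bands are compared, a lower value in one age band could be taken for worse performance there when only the spread of CRT differs.

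Section 2.2 says the aim is to set Cap App normal values for later use in detecting perfusion abnormalities. Without an estimate of the offset, those norms cannot be related to manual CRT.

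**Working it through.** **The plan's own figure.** Half-width = 1.96 × SD/√n. With SD 0.663 s (15.3): n = 48 gives 0.1876 and n = 240 gives 0.0839, matching the stated ±0.188 s and ±0.084 s. These describe mean CRT. No precision is stated for correlation or agreement.

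**Uniform offset.** Let S be the SD of true CRT between children, e the SD of reference error and d a constant offset. For an app with no random error, leaving press variation aside for now:

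- r = S/√(S² + e²), which does not contain d.
- Lin's concordance = 2S²/(2S² + e² + d²), which does.

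With S = 0.663 and e = 0.3 (assumed), r = 0.663/√(0.4396 + 0.09) = 0.911 for every d. Concordance is 0.907, 0.852, 0.721 and 0.446 for d = 0, 0.25, 0.5 and 1.0 s. The offsets are illustrative, since the pilot gives no size. Rescaling every reading leaves r unchanged in the same way.

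**Ceiling for an error-free app.** Because the methods time different presses, press-to-press variation (SD p) enters both sides, and computer error e only one:

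r = S²/√[(S² + p²)(S² + p² + e²)]

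For means of four presses, replace p² by p²/4 and e² by e²/4. The documents give neither p nor e. I assume e = 0.1 s and p = 0.40, 0.49 or 0.556 s. They also do not say what kind of SD 0.663 s is, so both readings are shown.

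| Reading of 0.663 s | S | p | r, single press | r, four-press means |
|---|---|---|---|---|
| Total (S² + p²) | 0.53 | 0.40 | 0.63 | 0.87 |
| Total | 0.45 | 0.49 | 0.45 | 0.77 |
| Total | 0.36 | 0.556 | 0.29 | 0.62 |
| Between-child | 0.663 | 0.40 | 0.73 | 0.91 |
| Between-child | 0.663 | 0.49 | 0.64 | 0.88 |
| Between-child | 0.663 | 0.556 | 0.58 | 0.85 |

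First row: S² = 0.2809 and p² = 0.16, so r = 0.2809/√(0.4409 × 0.4509) = 0.63.

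**Same app, two age bands.** Keep p = 0.40 and e = 0.1 and change only the spread. S = 0.53 gives 0.63. S = 0.36 gives 0.1296/√(0.2896 × 0.2996) = 0.44. The app is perfect in both.

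**What a paired analysis would deliver.** The SD of the per-child difference is not in the documents, so I take 0.3, 0.5 and 0.663 s. Half-width for the mean difference = t × SD/√n. For each limit of agreement it is t × SD × √[1/n + 1.96²/(2(n − 1))].

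| n | Mean difference | Each limit of agreement |
|---|---|---|
| 48 | ±0.087 / 0.145 / 0.193 s | ±0.150 / 0.250 / 0.331 s |
| 240 | ±0.038 / 0.064 / 0.084 s | ±0.065 / 0.109 / 0.144 s |

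**The case against.** The word may be meant loosely, it belongs to the last of three secondary aims, and 15.1 does plan a within-subject comparison. That is fair on weight. It does not supply a method: 15.1 names no statistic, and 15.3 confines the agreement tools to annotators.

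Several stronger readings are tempting and should not be taken from the documents.

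- A reader might infer that the correlation *will* be low. The documents do not show this. Four-press means give a perfect app 0.62 to 0.91 across the scenarios above, and the low values need single-press analysis with larger press noise. The plan does not say which presses enter the correlation.
- A reader might infer that spread within an age band is small compared with press variation. Neither figure is given, and section 2.0 notes significant sex as well as age variation in healthy people; the sex variation remains within a band.
- A reader might infer that none of the pilot's error can reach the coefficient. Only a uniform shift or rescaling is invisible. Over-reading that differs by skin tone can change r, though r would not reveal its source.
- A reader might infer that the aim could be wrongly declared met or failed. Section 3.2 sets no threshold, so there is nothing to meet or fail.

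The SD of 0.663 s is also weak ground. It appears to come from the adult pilot, and its method and type are not stated. The table is therefore a range under assumptions, not a forecast.

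**Conclusion.** The point holds in this form. Correlation alone cannot show the uniform part of the offset that the pilot reports, and no Cap App versus manual agreement analysis is specified. Followed as written, the plan could report a good correlation and leave that offset unquantified. The first part is algebra and needs no assumed figure.

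The second part is conditional. Because the methods use separate presses, r can be low for an error-free app: about 0.29 to 0.63 on single presses if 0.663 s is the total SD, or 0.58 to 0.73 if it is the between-child SD. Four-press means raise these to about 0.62 to 0.87 or 0.85 to 0.91. All rest on assumed press SDs of 0.40 to 0.556 s and computer error of 0.1 s. It follows that a difference in r between age bands is not, by itself, evidence of a difference in the app.

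This should be changed. It concerns a secondary aim, but the same paired analysis would also serve the accuracy part of the primary endpoint.

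**What to change.** Reword the third part of 3.2 from correlation to agreement between Cap App and manual CRT. Add to 15.3:

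- The paired difference, Cap App minus computer annotation, as the main comparison, with human annotation as a second one.
- The mean difference with 95% CI and Bland–Altman 95% limits of agreement, overall, by age band and by skin tone.
- An analysis that accounts for the repeated presses per child, stating whether the limits refer to single readings or per-child means. Press variation widens the limits too, and the repeats allow it to be separated.
- The correlation as a description only. A Deming slope pooled across ages is optional, since it may be imprecise over a narrow healthy range.

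The planned numbers can support this: at the assumed SDs the mean difference is known to within about ±0.09 to ±0.19 s per age band of 48. Precision by skin tone cannot be given in advance because no group sizes are stated.

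The cost is a small added analysis with no further measurements. This version (10/27/2022) postdates the stated recruitment window (August 25 to September 5, 2022), so record the agreement analysis as a dated addition made before the blinded measurements are analysed. If analysis has already begun, which the documents do not show, label it as added afterwards.

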4.0 Study Intervention(s)/Investigational Agent(s)

- 1.2 **Description:** Cap App – mobile smartphone application used to measure CRT. The CapApp is a smartphone mobile application created through a partnership with the University of Washington, The University of Toronto, and The University of Minnesota. Management of the application will primarily be the responsibility of The University of Washington Ubiquitous Computing Lab led by [name] and PhD candidate, [name]. Oversight of the project will be from The University of Toronto Assistant Professor of Computer Science, [name]. A standard Android smartphone running a custom smartphone application will be used for collecting fingertip videos, motion data, demographics (e.g., age, sex, temperature), and skin tone using the Fitzpatrick skin color scale. The app will start up and allow the user to enter a study ID and age, sex, race, skin tone, skin temperature, room temperature, core temperature, weight, vital signs (heart rate, blood pressure) and any underlying diagnosis. No other identifying information will be stored, including date of birth, name, audio, or fingerprint. The user is asked to place their right index finger on the

MEDICAL PROTOCOL (HRP-590)

PROTOCOL TITLE: Capillary Refill Time Measurement Utilizing Mobile Application (Cap App) in Children
VERSION DATE: 10/27/2022

front camera. Once the app confirms that the finger is correctly placed, it asks the user to apply pressure against the phone. When the app detects whether the user is applying enough pressure for the specified time, it asks the user to relax the pressure. A function to notate any required assistance for the child in pressing on the smartphone to measure the capillary refill will also be noted. This will be needed especially for younger children and infants as it may cause a difference in how to interpret the results of the measurement. The app collects accelerometer/gyroscope data and video recording of the fingertip. The fingertip recording will not collect fingerprint identification information. The collected data will be uploaded to the cloud server on a secure data storage platform, Box.

The device, as used in this study protocol, does not meet the criteria of a serious risk device under 21 CFR 812.3(m) and therefore is a non-significant risk (NSR) device. The device meets the criteria of a NSR-IDE for the following reasons:

- This device is not intended as an implant and does not present a potential for serious risk to health, safety, or welfare of a subject.
- Is not purported or represented to be for a use in supporting or sustaining human life and presents a potential for serious risk to the health, safety or welfare of a subject.
- Is not for a use of substantial importance in diagnosing, curing, mitigating, or treating disease, or otherwise preventing impairment of human health and does not present a potential for serious risk to the health, safety or welfare of a subject.
- Does not otherwise present a potential for serious risk to the health, safety or welfare of a subject.
- We will comply with the abbreviated requirements in 21 CFR 812.2(b).

1.3 Drug/Device Handling: The Cap App mobile software will be uploaded onto two smartphone devices. The smartphones will be locked with a passcode and only study team members will have access to that passcode.

Those devices will be stored in the Pediatric Emergency Department where only study personnel will have access to them for purposes of enrolling participants and collecting the study data.

As this device will be used at The Driven to Discover Research Facility at the Minnesota State Fair (2022), the device will be transferred and remain in possession of a study team meeting at all times.

- 4.1 Biosafety: NA
- 4.2 Stem Cells: NA
- 4.3 Fetal Tissue: NA

MEDICAL PROTOCOL (HRP-590)

PROTOCOL TITLE: Capillary Refill Time Measurement Utilizing Mobile Application (Cap App) in Children
VERSION DATE: 10/27/2022

5.0 Procedures Involved

5.1 Study Design: The study design will be a cross-sectional study. The observation will be to collect the CRT from a population of healthy pediatric participants. Participants who meet the inclusion criteria will have their CRT measured using both the manual measurement (to include both human and computer annotation) and mobile health application (Cap App).

Study Procedures: **Cap App CRT measurement:** Children will be placed in a seated position, and their hand resting on a table top in a resting position. The research assistant will use a smartphone with the mobile health application (Cap App) to measure the CRT. The phone will be placed on a tabletop with the front facing camera face up. The subject's index fingertip will be placed onto the camera of the smartphone with minimal pressure. The finger will then be pressed firmly against the camera for a total of 5 seconds and then released from firm pressure while still contacting the camera with instructions from the Cap App. The research assistant then presses "stop" on the Cap App device. The Cap App will then measure the amount of time it takes for blood to refill the capillary bed as evidenced by the signal return to normal of light shining on the capillary bed. This measurement will be kept blinded to the researcher and be uploaded to a secure web-based cloud server, Box, for analysis. To establish the reproducibility of the index test (or the ability of the test to be accurately replicated), the CRT will be repeated at least twice on the index fingertip with at least 15 seconds between tests, and twice on the index finger of the opposite hand, all within 30 to 60 seconds of each other.

Manual CRT measurement: Children will be placed in a seated position with their hand raised slightly above the level of the heart on a table. A tripod will be set up for the smartphone to video record the capillary refill test by facing the table from the top. The recording will begin, and audio will not be recorded. The research assistant will compress the index finger of the participant for 5 seconds with transparent plastic and then release the pressure, after which the plastic will be removed from the field of view of the camera. The camera recording will then be stopped once the research assistant has determined the color has returned to its original color. To establish the reproducibility of the index test (or the ability of the test to be accurately replicated), the CRT will be repeated at least twice on 1 fingertip with at least 15 seconds between tests, and twice on the index finger of the opposite hand, all within 30 to 60 seconds of each other. The video, without audio, will be stored in the University of Minnesota's secure online storage platform, Box. For analysis the research study team will complete the following:

- Human annotation from manual CRT measurement: The video will be annotated blindly by a separate research team member than the one who performs the CRT manual measurement. The CRT will be measured as the

MEDICAL PROTOCOL (HRP-590)

PROTOCOL TITLE: Capillary Refill Time Measurement Utilizing Mobile Application (Cap App) in Children

VERSION DATE: 10/27/2022

amount of time required for the index finger color to return to its pre-compressed color. The measurement will be annotated by a trained human from the video recording by measuring the CRT with a stopwatch, as is the current standard.

- Computer annotation from manual CRT measurement: The same video from the manual CRT measurement will be used for the computer annotation. A research team member will manually select a section of the finger for use in the analysis and then a computer will analyze the color using signal processing. This annotation will serve as the gold standard of what is possible for human visual CRT measurement.

Individually Identifiable Health Information: Electronic data collection forms will be used to collect all relevant variables to help interpret CRT measurements in the context of the healthy patient populations. In brief, the following is the information that will be collected:

1) For healthy participants:

- a. Demographics (race/ethnicity, gender, age).
- b. Temperature (environment, core, skin at finger).
- c. Clinical (weight, blood pressure, heart rate, oxygen saturation, skin tone)
- d. CRT measurement (manual video, Cap App)
- e. Any underlying diagnosis (medical history)

5.2 Study Duration:

- Total study length: 15 months including 3 months for protocol development and IRB approval, 6 months for data collection, and 6 months for data analysis.
- Individual participant: time expected to complete the study is 30 minutes; 20 minutes for enrollment screening and consent and 10 minutes for the CRT measurements

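### Section 5.1 describes hand position differently for Cap App and for the manual reference, so any effect of hand height would be inseparable from method in the accuracy comparison

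*Combined protocol and SAP*

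**What the plan says.** Section 5.1 gives each method its own positioning instruction. For the manual video: "Children will be placed in a seated position with their hand raised slightly above the level of the heart on a table". For Cap App: "Children will be placed in a seated position, and their hand resting on a table top in a resting position". The phone also lies on a tabletop with its camera upward. Neither this paragraph nor the device description in section 4.0 gives a Cap App height relative to the heart.

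Both manual readings carry the manual position. The stopwatch reading is taken from the video, and for the computer reading, "The same video from the manual CRT measurement will be used for the computer annotation".

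The listed data items include "CRT measurement (manual video, Cap App)" but not hand position. The list is introduced by "In brief, the following is the information that will be collected", so it may not be complete.

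Accuracy and precision of Cap App form the primary endpoint (section 3.1). Section 15.1 plans to compare manual and Cap App CRT within each subject. Section 15.3 expresses the primary outcome as mean CRT with 95% confidence intervals and gives half-widths for a mean.

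**The concern.** In a method comparison, conditions other than the method should be the same for both tests or should be recorded. Here the plan itself words one such condition differently for the two methods. It ties the reference test to heart level and leaves the device test without that anchor.

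If the heights differ and height matters, part of the Cap App minus manual difference would reflect where the hand was held. That part could look like app error, or it could offset real app error and hide it. The planned data could not show which.

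The question could arise in practice. Section 2.1 reports that in the adult pilot Cap App gave longer CRT than the manual method. This is not evidence of a height effect. But if an offset appears again in children, the study will have to interpret it, and this design could not say whether hand position contributed.

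**Working it through.** **1. The plan's own figure.** Section 15.3 gives a standard deviation of 0.663 s and half-widths of ±0.188 s (n = 48) and ±0.084 s (n = 240). With half-width = 1.96 × SD / √n:

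- n = 48: 1.96 × 0.663 / √48 = 0.1876 s, which rounds to 0.188 s.
- n = 240: 1.96 × 0.663 / √240 = 0.0839 s, which rounds to 0.084 s.

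Both reproduce. They describe a single mean. The plan gives no interval or margin for the paired difference, and section 15.3 does not say which method the 0.663 s describes. These figures therefore cannot be used to judge a position effect in the comparison.

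**2. The two procedures side by side (section 5.1).**

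- Posture: seated for both.
- Support: a table for both.
- Height relative to the heart: a little above it for manual; not stated for Cap App.
- Compression and release, manual: pressed "with transparent plastic and then release the pressure, after which the plastic will be removed from the field of view of the camera".
- Compression and release, Cap App: pressed on the camera, "then released from firm pressure while still contacting the camera with instructions from the Cap App".

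**3. What the comparison can estimate.** As a simple additive illustration, let a child's Cap App reading be T + a + g(h_A) and the manual reading T + m + g(h_M). T is the child's underlying CRT, a and m are the systematic errors of the two methods, and g(h) is any effect of hand height h. The mean paired difference then estimates

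(a − m) + mean of [g(h_A) − g(h_M)].

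The second term is zero if the heights coincide or if g is flat. Otherwise, with one prescribed position per method and position not recorded, only the sum can be estimated.

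**4. Can anything in the plan separate the terms?**

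- *Repeats.* Each method is repeated on both hands, but no repeat is assigned a second height, so averaging leaves the term in place.
- *A second comparator.* The stopwatch and computer readings share one video and so share h_M.
- *Adjustment.* Sections 15.1 and 15.3 have no term for position, and no section names it as a recorded item.
- *Sample size.* A larger n shrinks the random error around the sum and leaves the second term unchanged.

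**5. Size.** The document gives no value for g, for the share of children whose heights differ, or for the direction of any effect. No magnitude, added spread or change in correlation can be derived without inventing inputs, so none is given.

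**The case against.** The strongest reply is that no real difference has been shown. Both tests seat the child with the hand on a table, and the two sentences could describe the same set-up. The document names age, sex, skin tone and temperature as factors but never hand height. All of this stands, and it is why the point is conditional.

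Set-up detail may also sit elsewhere. Section 18.1 refers to SOPs, section 25.1 to informing staff about procedures, and the data list is introduced as a summary. This stands too: silence in the protocol does not prove that positioning varied. It does not reconcile two instructions that are worded differently within the protocol.

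The link to the primary endpoint is also looser than it may seem. Section 15.3 makes the primary outcome mean CRT, and the within-child comparison in section 15.1 has no stated estimator. That limits the reach of the point. Accuracy is still named in section 3.1, and the manual methods are the comparison the plan offers for it.

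A reader might infer more than the text supports:

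- *That the Cap App hand position is uncontrolled.* It is not: posture, support, resting hand and phone placement are fixed. Only height relative to the heart is unstated.
- *That the heights did differ, or that CRT was biased by a given amount.* Nothing in the document establishes either.
- *That the Cap App normal ranges are wrong.* A shift would be an error only against a target height, and none is defined. Ranges taken in the app's specified resting position describe the app as used in this study.

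**Conclusion.** The point holds as an inconsistency between two instructions for methods that are to be compared. It is minor, and correcting it is a cheap improvement. Its force rests on two conditions that the document neither establishes nor excludes: that the heights differ in at least some children, and that height affects CRT. If either fails, there is no bias. If both hold, the effect is aliased with method in the Cap App versus manual comparison whatever the sample size, and its size and direction are unknown.

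It would be a mistake to conclude that the accuracy result is invalid or that the sample-size figures are wrong. The half-widths reproduce and are untouched. What follows is narrower: as written, the paired difference cannot be assigned to the device alone on the strength of the design.

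**What to change.** **Section 5.1.** Reconcile the two paragraphs with one sentence covering both tests, for example: *For the Cap App and the manual test the hand is in the same position, on the same support, at [height relative to the heart, to be chosen by the investigators].* Noting the position at each reading is optional, as a check on adherence. The app is already planned to capture a related item: "A function to notate any required assistance for the child in pressing on the smartphone to measure the capillary refill will also be noted".

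**Section 15.3, for data already collected.** The only named enrolment window (section 11.1) closed on September 5, 2022, before this version dated 10/27/2022, so the change to section 5.1 cannot alter those readings. Report the positions actually used, if known, and add: *The Cap App minus manual difference may include a difference in hand position between the tests and is not attributed to device error alone.*

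**Cost.** A small wording change, one optional data field and a slightly more limited accuracy conclusion, with no extra participants, staff or visits. The differences in compression and release remain after this change, so it removes one avoidable difference between the methods, not all of them.
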